**Definitions:**

- Oral small molecules (OSMs): methotrexate, leflunomide, sulfasalazine, apremilast
- Tofacitinib monotherapy: initiation of tofacitinib with no other (pre-existing or new) DMARD prescriptions
- Tofacitinib combination therapy: initiation of tofacitinib with a concomitant (pre-existing or new) prescription of at least one OSM

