### Milestone 2:

The analyses stratified by mono- and combination therapy for this milestone will be completed when the sample reaches at least 100 initiators in both mono- and combination therapy groups.

Consider the demographic, patient, and disease characteristics of the tofacitinib monotherapy and combination therapy initiators in **Table 4**. Categorical variables will be examined using frequencies and proportions, and, when sample size allows for significance testing, differences across therapy patterns will be tested using chi-square or Fisher exact tests. Continuous variables will be summarized using descriptive statistics (n, mean, standard deviation, minimum, 25% percentile, median, 75% percentile, maximum). When sample size allows for significance testing, differences across therapy groups will be tested using Wilcoxon rank sum tests.

In **Table 5**, we will present the therapy status of initiators at the six-month follow-up visit.

**Table 6** will examine the outcomes of interest at the six-month follow-up visit. The change from baseline to six months in continuous outcomes will be analyzed using an analysis of covariance model with fixed effects for treatment group and baseline value. For continuous outcomes, we will not impute missing values. Also, for those discontinuing therapy prior to follow-up, we will use the value immediately prior to discontinuation as the follow-up value. We will present LS Means (standard error) for each therapy group as well as the difference in the LS Means (standard error), 95% CI and p-value. Binary outcomes will be presented as response rates with 95% CIs using normal approximation to binomial proportions. We will provide comparisons of response rates between groups with 95% CIs and p-values using normal approximation for the difference in binomial proportions. As a supportive analysis, treatment difference between the groups will be assessed using logistic regression models with treatment group as the sole covariate. For binary outcomes, we will impute non-response for missing values and for those patients discontinuing therapy prior to follow-up.

In **Table 7**, we will present summary statistics (n, mean (SD), [P0,P25,P50,P75,P100]) for continuous outcomes featured in Table 3 at baseline, six months, and the difference from baseline to six months overall and by therapy group.

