### **Characteristics of Interest:**

The following characteristics will be assessed on index date:

- Age
- Sex
- Race
- Work status
- BMI (continuous and categorical)
- Duration of PsA symptoms
- Time since PsA diagnosis
- Time since onset of PsO
- Physician-reported comorbidity history

- Cerebro-cardiovascular disease (CVD)a
  - Depression
  - Diabetes mellitus
  - Any cancer (excluding NMSC)
  - NMSC
  - HTN
  - Hyperlipidemia
  - Crohn's disease
  - Anxiety
  - Psoriasis
  - Fibromyalgia
  - Serious infections b
  - Metabolic syndrome
  - Ulcerative colitis
  - Uveitis
- Smoking status
  - Former, Current, Never
  - Number cigarettes smoked per day
  - Smoking duration
- Alcohol use
  - Yes/No
  - Number drinks per week
- Therapy history
  - History of prior biologic use
  - History of prior TNFi use
  - History of prior non-TNFi bDMARD use
  - History of prior OSM use
  - Current OSM use
    - Current MTX use
  - Current NSAID use
  - Current opioid use
  - Current aspirin use
  - Current prednisone use
- Disease activity measures
  - Tender joint count (28 and 68)
  - Swollen joint count (28 and 66)
  - Enthesitis
  - SPARCC count
  - LEI count
  - Dactylitis
  - Dactylitis count
  - Nail VAS
  - BSA (continuous and categorical)
  - CRP
  - ESR
  - Clinical global assessment of PsO (continuous and categorical).
- Composite measures
  - MDA

- DAPSA (continuous and categorical)
- cDAPSA (continuous and categorical)
- PASDAS
- CDAI (continuous and categorical)
- Patient reported outcome measures
  - Patient pain
  - Patient-reported fatigue
  - Patient global skin assessment
  - HAQ-DI
  - HAQ-S
  - EQ-5D
  - WPAI domains (4 categories)
- Psoriatic nail dystrophy
- Spinal mobility measures
  - Occiput to wall distance
  - Modified Schober

a CVD includes: cardiac revascularization procedure (CABG, stent, angioplasty), ventricular arrhythmia, cardiac arrest, myocardial infarction, acute coronary syndrome, unstable angina, other coronary artery disease, CHF (with and without hospitalization), stroke, transient ischemic attack, other CV, deep vein thrombosis, peripheral arterial disease, pulmonary embolism, and carotid artery disease

b Serious infections include: joint bursa infection, cellulitis, sinusitis, candida, diverticulitis, sepsis, pneumonia, bronchitis, gastroenteritis, meningitis, urinary tract infection, upper respiratory infection, tuberculosis, and other infection

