At the six-month follow-up visit, the following will be assessed:

Among those not in the specified disease activity state, achievement of:

- Minimal Disease Activity
- Body Surface Area Score of 0
- PASDAS < 3.2
- Resolution of enthesitis
- Resolution of dactylitis
- Clinical Global Assessment of PsO – achievement of “Clear” or “Almost Clear”

Baseline to six months change in:

- cDAPSA
- DAPSA
- PASDAS
- HAQ-DI
- Low Disease Activity as defined by cDAPSA (cDAPSA ≤ 13)
- BSA
- CDAI
- Tender joint count (68)
- Swollen joint count (66)
- Patient global skin assessment
- Patient pain
- Patient fatigue
- Clinical Global Assessment of PsO
- WPAI Domains

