Moderate				
Severe				
HAQ-DI, n, Mean (SD), [P0,P25,P50,P75,P100]				
HAQ-S, n, Mean (SD), [P0,P25,P50,P75,P100]				
EQ-5D, n, Mean (SD), [P0,P25,P50,P75,P100]				
WPAI Domains (%), n, Mean (SD), [P0,P25,P50,P75,P100]				
Work Time Missed				
Impairment While Working				
Overall Work Impairment				
Activity Impairment				
Spinal Mobility Measures (cm), n, Mean (SD), [P0,P25,P50,P75,P100]				
Occiput to Wall Distance				
Modified Schober				

SD = standard deviation, P0 = minimum, P25 = 25th percentile, P50 = median, P75 = 75th percentile, P100 = maximum

a p-values from chi-square or Fisher exact tests for categorical variables and from Wilcoxon rank-sum tests for continuous variables, included for descriptive purposes only

b History of cardiovascular disease includes history of: hypertension, hyperlipidemia, cardiac revascularization procedure (CABG, stent, angioplasty), ventricular arrhythmia, cardiac arrest, myocardial infarction, acute coronary syndrome, unstable angina, CHF (with and without hospitalization), stroke, transient ischemic attack, other CV, deep vein thrombosis, peripheral arterial disease, peripheral arterial thrombosis, urgent peripheral revascularization, peripheral ischemia/gangrene, pulmonary embolism, carotid artery disease, and hemorrhage.

c Malignancy includes breast cancer, lung cancer, lymphoma, skin cancer (squamous cell), and other cancers.

d Serious infections include the following: joint/bursa infection, cellulitis, sinusitis, diverticulitis, sepsis, pneumonia, bronchitis, gastroenteritis, meningitis, urinary tract infection, upper respiratory infection, tuberculosis, and other infections.

e Biologics: Humira, Enbrel, Cimzia, Simponi, Remicade, Orencia, Taltz, Cosentyx, Stelara

f TNFs: Humira, Enbrel, Cimzia, Simponi, Remicade

g non-TNFs: Orencia, Taltz, Cosentyx, Stelara

h cDMARDs: MTX, Arava, Azulfidine, Otezla

 Clinical Global Assessment of PsO is scored on a five-point scale from 0-4, with corresponding interpretations of Clear, Almost Clear, Mild, Moderate, and Severe, respectively.

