**Table 5. Therapy status six months post-initiation**

	Overall	Mono	Combo	p -value a
All Patients, N				
Remain on tofacitinib, n (%)				
Discontinued tofacitinib, n (%) b				
Switched to a bDMARD, n (%) c				
Added OSM, n (%)				
Discontinued OSM, n (%)				

a p-value from chi-square testb This group consists of those discontinuing tofacitinib and not initiating a bDMARD at or prior to the six-month follow-up visitc This group consists of those discontinuing tofacitinib and initiating a bDMARD at or prior to the six-month follow-up visit

**Table 6.** Disease activity outcomes at six months

	Mono	Combo	Mono vs Combo		
	Binary Outcomes	Response Rate (95% CI) a	Response Rate (95% CI) a	Rate Difference (95% CI) a	p-value a
Achievement of:					
LDA (cDAPSA)					
Minimal Disease Activity					
Body Surface Area Score of 0					
PASDAS < 3.2					
Resolution of enthesitis					
Resolution of dactylitis					
Clinical Global Assessment of PsO – Clear or Almost Clear					
Continuous Outcomes		LS Means (SE)	LS Means (SE)	Δ LS Means (SE) 95% CI	
Baseline to six-month change in:					
cDAPSA					
DAPSA					
PASDAS					
HAQ-DI					
BSA					
CDAI					
Tender joint count					
Swollen joint count					
Patient global skin assessment					
Patient pain					
Patient fatigue					
Clinical Global Assessment of PsO					
Work Time Missed					
Impairment While Working					
Overall Work Impairment					
Activity Impairment					

a 95% CI for the response rate and 95% CI and p-value for the rate difference were based on normal approximation to binomial proportions. OR (95% CI) was based on a logistic regression model with treatment group as the sole covariate

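### Table 6 compares monotherapy and combination therapy without adjustment for binary outcomes, and its supportive logistic model only repeats the crude result

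*SAP*

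**What the plan says.** Protocol section 9.1 describes a retrospective observational cohort drawn from a registry. The SAP (Definitions) forms the groups from prescriptions; combination therapy, for example, is "initiation of tofacitinib with a concomitant (pre-existing or new) prescription of at least one OSM". Both Protocol objectives are descriptive, but SAP Objective 2 adds a comparison of the two groups, and Protocol sections 9.5 and 9.7 also foresee between-group comparisons.

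The Table 6 analyses are set out in SAP Milestone 2:

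- **Seven binary outcomes.** Crude response rates and rate differences by normal approximation, with 95% CIs and p-values. As support, "treatment difference between the groups will be assessed using logistic regression models with treatment group as the sole covariate". The Table 6 footnote repeats this: "OR (95% CI) was based on a logistic regression model with treatment group as the sole covariate".
- **Sixteen continuous outcomes.** "an analysis of covariance model with fixed effects for treatment group and baseline value". Protocol section 9.7 specifies the same model.
- **Baseline comparison (Table 4).** Where numbers allow, "differences across therapy patterns will be tested using chi-square or Fisher exact tests", with rank-sum tests for continuous variables. The footnote says these p-values are "included for descriptive purposes only". The Table 6 footnote carries no such label.

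The Characteristics of Interest list holds several plausible drivers of prescribing, such as "History of prior biologic use", disease duration, prednisone use, comorbidities and baseline activity. Six of the seven binary outcomes are restricted as follows: "Among those not in the specified disease activity state, achievement of". Low disease activity by cDAPSA is listed outside that restriction.

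**The concern.** Rheumatologists decide who receives tofacitinib alone and who receives it with an oral small molecule. If that decision is related to prognosis, a crude difference in response mixes the effect of the regimen with the difference between the patients. Table 4 would let a reader see a measured imbalance, but no planned model shows how much of a Table 6 difference it explains.

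The supportive analysis adds to the problem. A reader may take agreement between the rate difference and the odds ratio as corroboration, although both come from the same four counts and must agree apart from scale.

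**Working it through.** **1. The plan's own precision figure, as a yardstick.** Protocol section 9.5 states a half width below 16 points for a difference in proportions; the current target is 73 per group (section 5, amendment 2). With half width = 1.96 × √(2p(1−p)/n):

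- p = 0.5, n = 73: 16.2 points, just above the stated bound (n = 80 gives 15.5).
- p = 0.3, n = 73: 14.9 points.
- p = 0.3 at the 59 and 55 patients with a six-month visit in the SAP feasibility table: 1.96 × √(0.21 × (1/59 + 1/55)) = 16.8 points.

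**2. The treatment-only logistic model.** Two parameters fit two proportions, so the model is saturated. With assumed counts of 28/73 and 20/73, the cross-product odds ratio is (28 × 53)/(45 × 20) = 1.6489, and its standard error is √(1/28 + 1/45 + 1/20 + 1/53) = 0.356. The fitted logistic model returns the same two numbers.

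**3. Size of possible bias, binary outcomes.** All inputs are assumed: response is 20% with two or more prior biologics and 40% otherwise, there is no true group effect, and there are 73 per group. The expected rate is 0.2c + 0.4(1−c), where c is the share with that history.

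| Share, mono / combo | Rate, mono / combo | Bias (points) | Crude coverage |
|---|---|---|---|
| 55% / 45% | 0.29 / 0.31 | −2 | 0.942 |
| 60% / 40% | 0.28 / 0.32 | −4 | 0.918 |
| 70% / 40% | 0.26 / 0.32 | −6 | 0.876 |

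Coverage uses SE = √(0.21 × 2/73) = 0.0759. Reversing the second case (40% / 60%) gives about +4 points. The bias does not shrink as the groups grow.

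**4. What adjustment does.** Simulation with 3,000 runs per case and the same assumptions. The logistic model has six slopes: treatment, prior biologics (two), baseline measure, duration and age. Results are standardised rate differences, listed in the order of the three cases above.

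| 73 per group | Bias | Coverage | Half width | RMSE |
|---|---|---|---|---|
| Crude | −0.018, −0.039, −0.059 | 0.940, 0.915, 0.870 | 0.148, 0.147, 0.146 | 0.077, 0.085, 0.095 |
| Adjusted | 0.002, 0.001, 0.002 | 0.945, 0.942, 0.941 | 0.145, 0.147, 0.150 | 0.075, 0.077, 0.078 |

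The confounder is in the adjusted model, so its low bias is expected. Three further settings test the limits:

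- **No imbalance:** RMSE 0.0754 crude and 0.0748 adjusted, so adjustment costs nothing.
- **A second confounder (55% / 45%, 20-point effect) left out of the model:** bias −0.041, −0.060, −0.079 crude, and −0.021, −0.020, −0.020 adjusted.
- **Fewer evaluable patients:** at 40 per group (24 responders, 4 per slope), RMSE is 0.105, 0.111, 0.119 crude and 0.105, 0.109, 0.110 adjusted. At 25 per group (15 responders, 2.5 per slope), it is 0.133, 0.133, 0.140 crude and 0.136, 0.133, 0.140 adjusted, with 1.5% to 2.5% non-convergence.

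**5. ANCOVA.** Assume the history shifts change by 0.4 SD beyond what the baseline value explains. By hand the bias is 0.4 × 0.10, 0.20 or 0.30 = 0.04, 0.08 or 0.12 SD. Simulation (4,000 runs, 73 per group) gives 0.040, 0.084 and 0.125 SD, coverage 0.942, 0.922 and 0.887, and half width 0.334 SD. With the added covariates the bias is 0.001, 0.004 and 0.006 SD, coverage 0.949, 0.950 and 0.952, and half width 0.334, 0.339 and 0.349 SD.

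**The case against.** The strongest reply is that the study is descriptive. The Protocol objectives are to describe, section 9.5 calls it an estimation study, section 9.7 fixes crude differences, and no causal claim is made. As an interval for the crude difference itself, the planned CI covers at 0.946 to 0.948 in all three cases above. This answers the Protocol but not the SAP, which sets out to compare the groups and attaches p-values to that comparison.

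The magnitudes are invented, and two of the three cases are small next to the half width. That stands, and it limits how serious the point can be called.

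Most binary outcomes will also have fewer than 73 evaluable patients per group, because six exclude patients already in the target state. At 40 per group, crude coverage is 0.941, 0.928, 0.903 and adjusted 0.934, 0.926, 0.930; at 25 it is 0.933, 0.923, 0.907 and 0.920, 0.926, 0.910. So at 40 per group the gain is confined to the largest imbalance, and at 25 there is essentially none. This also stands and calls for a sparse-data rule. The restriction itself changes the denominators; it does not balance the groups among those who remain.

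The one group difference the documents do show is attendance: six-month visits in 59/132 (44.7%) against 55/81 (67.9%), z = 3.30. Recent starts may explain part of it. Outcome regression among attenders need not remove selection of this kind, so adjustment is not a complete answer. Protocol section 9.9 breaks off in the copy reviewed and may hold a caveat, but a caveat would not change the models.

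A lighter remedy would be to label the contrast unadjusted and descriptive and drop the p-values. That fits the Protocol, but it leaves SAP Objective 2 without an interpretable comparison and keeps a supportive model that supports nothing.

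**Conclusion.** The concern holds. That the binary comparisons are unadjusted, that the supportive logistic model duplicates the crude table, and that the ANCOVA adjusts for baseline value alone all follow from the text and need no assumption.

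The harm is conditional. The documents do not show whether prior treatment, duration or activity differ between the groups, or in which direction. Under the assumed inputs the bias is 2 to 6 points at a half width of about 15, or 0.04 to about 0.12 SD at a half width of 0.33 SD. That is modest for imbalances of 10 to 20 points and material at 30. The point should be fixed before the stratified analysis is run. It does not undermine the descriptive results for all initiators.

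**What to change.** In SAP Milestone 2 and the Table 6 footnote:

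1. Replace the treatment-only logistic model with one pre-specified adjusted model per binary outcome, and report the standardised rate difference with its 95% CI. Add a column for it; the Table 6 shell has none for the odds ratio its footnote cites.
2. Fix a short covariate list from Characteristics of Interest in advance, not after seeing Table 4. An example is number of prior biologics (0/1/2+), one named PsA duration measure, age, and one baseline measure per outcome: cDAPSA for LDA, MDA and PASDAS; BSA for the two skin outcomes; one enthesitis count; dactylitis count. Prior OSM use deserves consideration, because the groups differ by OSM prescription. The final list is for the sponsor's statistician.
3. Add the same covariates to the ANCOVA, or report that version as supportive.
4. Keep the crude differences with 95% CIs, labelled unadjusted and descriptive, without p-values.
5. State a sparse-data rule under which only the labelled crude difference is shown. About 4 responders and 4 non-responders per slope is one example; the results at 40 per group suggest little gain at that level.
6. State a missing-covariate rule, such as multiple imputation, or complete cases with the number excluded shown.

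The cost is SAP text, a revised table shell and model code; no new data are needed. Protocol section 9.7 fixes the ANCOVA and sends major analysis changes to an amendment, so replacing it may require one, while a supportive version may not. Some intervals will widen slightly, and unmeasured confounding and selection by attendance will remain and should be acknowledged.

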### **Characteristics of Interest:**

The following characteristics will be assessed on index date:

- Age
- Sex
- Race
- Work status
- BMI (continuous and categorical)
- Duration of PsA symptoms
- Time since PsA diagnosis
- Time since onset of PsO
- Physician-reported comorbidity history

- Cerebro-cardiovascular disease (CVD)a
  - Depression
  - Diabetes mellitus
  - Any cancer (excluding NMSC)
  - NMSC
  - HTN
  - Hyperlipidemia
  - Crohn's disease
  - Anxiety
  - Psoriasis
  - Fibromyalgia
  - Serious infections b
  - Metabolic syndrome
  - Ulcerative colitis
  - Uveitis
- Smoking status
  - Former, Current, Never
  - Number cigarettes smoked per day
  - Smoking duration
- Alcohol use
  - Yes/No
  - Number drinks per week
- Therapy history
  - History of prior biologic use
  - History of prior TNFi use
  - History of prior non-TNFi bDMARD use
  - History of prior OSM use
  - Current OSM use
    - Current MTX use
  - Current NSAID use
  - Current opioid use
  - Current aspirin use
  - Current prednisone use
- Disease activity measures
  - Tender joint count (28 and 68)
  - Swollen joint count (28 and 66)
  - Enthesitis
  - SPARCC count
  - LEI count
  - Dactylitis
  - Dactylitis count
  - Nail VAS
  - BSA (continuous and categorical)
  - CRP
  - ESR
  - Clinical global assessment of PsO (continuous and categorical).
- Composite measures
  - MDA

- DAPSA (continuous and categorical)
- cDAPSA (continuous and categorical)
- PASDAS
- CDAI (continuous and categorical)
- Patient reported outcome measures
  - Patient pain
  - Patient-reported fatigue
  - Patient global skin assessment
  - HAQ-DI
  - HAQ-S
  - EQ-5D
  - WPAI domains (4 categories)
- Psoriatic nail dystrophy
- Spinal mobility measures
  - Occiput to wall distance
  - Modified Schober

a CVD includes: cardiac revascularization procedure (CABG, stent, angioplasty), ventricular arrhythmia, cardiac arrest, myocardial infarction, acute coronary syndrome, unstable angina, other coronary artery disease, CHF (with and without hospitalization), stroke, transient ischemic attack, other CV, deep vein thrombosis, peripheral arterial disease, pulmonary embolism, and carotid artery disease

b Serious infections include: joint bursa infection, cellulitis, sinusitis, candida, diverticulitis, sepsis, pneumonia, bronchitis, gastroenteritis, meningitis, urinary tract infection, upper respiratory infection, tuberculosis, and other infection

At the six-month follow-up visit, the following will be assessed:

Among those not in the specified disease activity state, achievement of:

- Minimal Disease Activity
- Body Surface Area Score of 0
- PASDAS < 3.2
- Resolution of enthesitis
- Resolution of dactylitis
- Clinical Global Assessment of PsO – achievement of “Clear” or “Almost Clear”

Baseline to six months change in:

- cDAPSA
- DAPSA
- PASDAS
- HAQ-DI
- Low Disease Activity as defined by cDAPSA (cDAPSA ≤ 13)
- BSA
- CDAI
- Tender joint count (68)
- Swollen joint count (66)
- Patient global skin assessment
- Patient pain
- Patient fatigue
- Clinical Global Assessment of PsO
- WPAI Domains

**Feasibility Assessment and Projections:**

Using the October 1, 2021 version of the PsA registry, we have identified the following therapy patterns among initiators of tofacitinib

	Eligible Initiations, N (%)
All tofacitinib initiations	213
Monotherapy	132 (62.0)
Combination with OSMs only	81 (38.0)
Combination with MTX	58 (71.6)

	Monotherapy	Combination with OSMs
Eligible Initiators	132	81
Six-month visit	59 (44.7%)	55 (67.9%)

**Shell Tables****Table 1.** Patient demographic characteristics among all tofacitinib initiators

All Patients, N	Overall
Age (years), n, Mean (SD), [P0,P25,P50,P75,P100]	
Female, n/N (%)	
Race, n/N (%)	
White	
Black	
Asian	
Other	
Work Status, n/N (%)	
Full Time/Part Time	
Retired	
Disabled	
Other	
BMI (kg/m  ), n, Mean (SD), [P0,P25,P50,P75,P100]	
BMI Category (kg/m  ), n/N (%)	
< 25	
25 to < 30	
30 +	
Duration of PsA Symptoms (years), n, Mean (SD), [P0,P25,P50,P75,P100]	
Time Since PsA Diagnosis (years), n, Mean (SD), [P0,P25,P50,P75,P100]	

All Patients, N	Overall
Time Since PsO Onset (years), n, Mean (SD), [P0,P25,P50,P75,P100]	
Psoriasis, n/N (%)	
Psoriatic Nail Dystrophy, n/N (%)	
History of Comorbidities, n/N (%)	
CVD b	
Depression	
Diabetes	
Malignancy c	
NMSC	
Hypertension	
Hyperlipidemia	
Crohns Disease	
Anxiety	
Fibromyalgia	
Serious Infections d	
Metabolic Syndrome	
Ulcerative Colitis	
Uveitis	
Smoking Status, n/N (%)	
Never	
Previous	
Current	
Cigarettes per day, n, Mean (SD), [P0,P25,P50,P75,P100]	
Smoking duration, n, Mean (SD), [P0,P25,P50,P75,P100]	
Alcohol Use, n/N (%)	
Number drinks per week, n, Mean (SD), [P0,P25,P50,P75,P100]	
Prior Biologics, n, Mean (SD), [P0,P25,P50,P75,P100]	
Number of Prior Biologics, n/N (%)	
0	
1	
2 +	
Prior TNFs, n, Mean (SD), [P0,P25,P50,P75,P100]	
Number of Prior TNFs, n/N (%)	
0	
1	
2 +	
Prior non-TNFs, n, Mean (SD), [P0,P25,P50,P75,P100]	
Number of Prior non-TNFs, n/N (%)	

All Patients, N	Overall
0	
1	
2 +	
Prior OSMs, n, Mean (SD), [P0,P25,P50,P75,P100]	
Number of Prior OSMs, n/N (%)	
0	
1	
2 +	
Current OSM Use, n/N (%)	
Current MTX Use, n/N (%)	
Current NSAID Use, n/N (%)	
Current Opioid Use, n/N (%)	
Current Aspirin Use, n/N (%)	
Prednisone Use, n/N (%)	
None	
Missing Dose	
Dose < 10 mg	
Dose $\geq$ 10 mg	
Tender Joints (28), n, Mean (SD), [P0,P25,P50,P75,P100]	
Tender Joints (68), n, Mean (SD), [P0,P25,P50,P75,P100]	
Swollen Joints (28), n, Mean (SD), [P0,P25,P50,P75,P100]	
Swollen Joints (66), n, Mean (SD), [P0,P25,P50,P75,P100]	
Enthesitis, n/N (%)	
SPARCC Enthesitis Count, n, Mean (SD), [P0,P25,P50,P75,P100]	
LEI Count, n, Mean (SD), [P0,P25,P50,P75,P100]	
Dactylitis, n/N (%)	
Dactylitis Count, n, Mean (SD), [P0,P25,P50,P75,P100]	
CDAI, n, Mean (SD), [P0,P25,P50,P75,P100]	
CDAI Category, n/N (%)	
Remission (CDAI $\leq$ 2.8)	
Low (2.8 < CDAI $\leq$ 10)	
Moderate (10 < CDAI $\leq$ 22)	
High (22 < CDAI)	
Minimal Disease Activity, n/N (%)	
DAPSA, n, Mean (SD), [P0,P25,P50,P75,P100]	
DAPSA Category, n/N (%)	
DAPSA $\leq$ 4	
4 < DAPSA $\leq$ 14	

All Patients, N	Overall
14 < DAPSA ≤ 28	
28 < DAPSA	
cDAPSA, n, Mean (SD), [P0,P25,P50,P75,P100]	
cDAPSA Category, n/N (%)	
cDAPSA ≤ 3	
3 < cDAPSA ≤ 13	
13 < cDAPSA ≤ 27	
27 < cDAPSA	
PASDAS, n, Mean (SD), [P0,P25,P50,P75,P100]	
PASDAS ≤ 3.2	
3.2 < PASDAS ≤ 4.2	
4.2 < PASDAS ≤ 6	
6 < PASDAS	
Nail VAS, n, Mean (SD), [P0,P25,P50,P75,P100]	
Body Surface Area (%), n, Mean (SD), [P0,P25,P50,P75,P100]	
BSA Category (%), n/N (%)	
0	
> 0 to < 3	
3 to < 10	
≥ 10	
CRP (mg/L), n, Mean (SD), [P0,P25,P50,P75,P100]	
ESR (mm/hr), n, Mean (SD), [P0,P25,P50,P75,P100]	
Patient Pain (0-100 VAS), n, Mean (SD), [P0,P25,P50,P75,P100]	
Patient Fatigue (0-100 VAS), n, Mean (SD), [P0,P25,P50,P75,P100]	
Patient Global Skin Assessment (0-100 VAS), n, Mean (SD), [P0,P25,P50,P75,P100]	
Clinical Global Assessment of PsO  , n, Mean (SD), [P0,P25,P50,P75,P100]	
Clinical Global Assessment of PsO  Category, n/N (%)	
Clear/Almost Clear	
Mild	
Moderate	
Severe	
HAQ-DI, n, Mean (SD), [P0,P25,P50,P75,P100]	
HAQ-S, n, Mean (SD), [P0,P25,P50,P75,P100]	
EQ-5D, n, Mean (SD), [P0,P25,P50,P75,P100]	
WPAI Domains (%), n, Mean (SD), [P0,P25,P50,P75,P100]	
Work Time Missed	
Impairment While Working	
Overall Work Impairment	

All Patients, N	Overall
Activity Impairment	
Spinal Mobility Measures (cm), n, Mean (SD), [P0,P25,P50,P75,P100]	
Occiput to Wall Distance	
Modified Schober	

SD = standard deviation, P0 = minimum, P25 = 25th percentile, P50 = median, P75 = 75th percentile, P100 = maximum

a p-values from chi-square or Fisher exact tests for categorical variables and from Wilcoxon rank-sum tests for continuous variables, included for descriptive purposes only

b History of cardiovascular disease includes history of: hypertension, hyperlipidemia, cardiac revascularization procedure (CABG, stent, angioplasty), ventricular arrhythmia, cardiac arrest, myocardial infarction, acute coronary syndrome, unstable angina, CHF (with and without hospitalization), stroke, transient ischemic attack, other CV, deep vein thrombosis, peripheral arterial disease, peripheral arterial thrombosis, urgent peripheral revascularization, peripheral ischemia/gangrene, pulmonary embolism, carotid artery disease, and hemorrhage.

c Malignancy includes breast cancer, lung cancer, lymphoma, skin cancer (squamous cell), and other cancers.

d Serious infections include the following: joint/bursa infection, cellulitis, sinusitis, diverticulitis, sepsis, pneumonia, bronchitis, gastroenteritis, meningitis, urinary tract infection, upper respiratory infection, tuberculosis, and other infections.

e Biologics: Humira, Enbrel, Cimzia, Simponi, Remicade, Orencia, Taltz, Cosentyx, Stelara

f TNFs: Humira, Enbrel, Cimzia, Simponi, Remicade

g non-TNFs: Orencia, Taltz, Cosentyx, Stelara

h cDMARDs: MTX, Arava, Azulfidine, Otezla

i Clinical Global Assessment of PsO is scored on a five-point scale from 0-4, with corresponding interpretations of Clear, Almost Clear, Mild, Moderate, and Severe, respectively.

**Table 2.** Therapy status six months post-initiation

All Patients, N	Overall
Remain on tofacitinib, n (%)	
Discontinued tofacitinib, n (%) a	
Switched to a bDMARD, n (%) b	

a This group consists of those discontinuing tofacitinib and not initiating a bDMARD at or prior to the six-month follow-up visit

b This group consists of those discontinuing tofacitinib and initiating a bDMARD at or prior to the six-month follow-up visit

**Table 3.** Summary statistics of continuous outcomes at baseline, six months, and change from baseline to six months

All Initiators, N	Overall
Achievement of:	Response Rate (95% CI)
LDA (cDAPSA)	
Minimal Disease Activity	
Body Surface Area Score of 0	
PASDAS < 3.2	
Resolution of enthesitis	
Resolution of dactylitis	
Clinical Global Assessment of PsO – Clear or Almost Clear	

		Overall
		n, mean (SD), [P0,P25,P50,P75,P100]
cDAPSA	Baseline	
	Six Months	
	Difference a	
DAPSA	Baseline	
	Six Months	
	Difference a	
PASDAS	Baseline	
	Six Months	
	Difference a	
HAQ-DI	Baseline	
	Six Months	
	Difference a	
BSA	Baseline	
	Six Months	
	Difference a	
CDAI	Baseline	
	Six Months	
	Difference a	
Tender joint count (68)	Baseline	
	Six Months	
	Difference a	
Swollen joint count (66)	Baseline	
	Six Months	
	Difference a	
Patient global skin assessment	Baseline	
	Six Months	
	Difference a	
Patient pain	Baseline	
	Six Months	
	Difference a	
Patient fatigue	Baseline	
	Six Months	
	Difference a	

		Overall
Clinical Global Assessment of PsO	Baseline	
	Six Months	
	Difference a	
Work time missed	Baseline	
	Six Months	
	Difference a	
Impairment while working	Baseline	
	Six Months	
	Difference a	
Overall work impairment	Baseline	
	Six Months	
	Difference a	
Activity impairment	Baseline	
	Six Months	
	Difference a	

a Calculated as six-month value minus baseline value

**Table 4.** Patient demographic characteristics by monotherapy and combination therapy, among all tofacitinib initiators

	Overall	Mono	Combo	p-value
All Patients, N				
Age (years), n, Mean (SD), [P0,P25,P50,P75,P100]				
Female, n/N (%)				
Race, n/N (%)				
White				
Black				
Asian				
Other				
Work Status, n/N (%)				
Full Time/Part Time				
Retired				
Disabled				
Other				
BMI (kg/m  ), n, Mean (SD), [P0,P25,P50,P75,P100]				
BMI Category (kg/m  ), n/N (%)				
< 25				
25 to < 30				
30 +				
Duration of PsA Symptoms (years), n, Mean (SD), [P0,P25,P50,P75,P100]				
Time Since PsA Diagnosis (years), n, Mean (SD), [P0,P25,P50,P75,P100]				
Time Since PsO Onset (years), n, Mean (SD), [P0,P25,P50,P75,P100]				
Psoriasis, n/N (%)				
Psoriatic Nail Dystrophy, n/N (%)				
History of Comorbidities, n/N (%)				
CVD b				
Depression				
Diabetes				
Malignancy c				
NMSC				
Hypertension				
Hyperlipidemia				
Crohns Disease				
Anxiety				
Fibromyalgia				
Serious Infections d				
Metabolic Syndrome				

	Overall	Mono	Combo	p-value
Ulcerative Colitis				
Uveitis				
Smoking Status, n/N (%)				
Never				
Previous				
Current				
Cigarettes per day, n, Mean (SD), [P0,P25,P50,P75,P100]				
Smoking Duration, n, Mean (SD), [P0,P25,P50,P75,P100]				
Alcohol Use, n/N (%)				
Number drinks per week, n, Mean (SD), [P0,P25,P50,P75,P100]				
Prior Biologics, n, Mean (SD), [P0,P25,P50,P75,P100]				
Number of Prior Biologics, n/N (%)				
0				
1				
2 +				
Prior TNFs, n, Mean (SD), [P0,P25,P50,P75,P100]				
Number of Prior TNFs, n/N (%)				
0				
1				
2 +				
Prior non-TNFs, n, Mean (SD), [P0,P25,P50,P75,P100]				
Number of Prior non-TNFs, n/N (%)				
0				
1				
2 +				
Prior OSMs, n, Mean (SD), [P0,P25,P50,P75,P100]				
Number of Prior OSMs, n/N (%)				
0				
1				
2 +				
Current OSM Use, n/N (%)				
Current MTX Use, n/N (%)				
Current NSAID Use, n/N (%)				
Current Opioid Use, n/N (%)				
Current Aspirin Use, n/N (%)				
Prednisone Use, n/N (%)				
None				
Missing Dose				

	Overall	Mono	Combo	p-value
Dose < 10 mg				
Dose $\geq$ 10 mg				
Tender Joints (28), n, Mean (SD), [P0,P25,P50,P75,P100]				
Tender Joints (68), n, Mean (SD), [P0,P25,P50,P75,P100]				
Swollen Joints (28), n, Mean (SD), [P0,P25,P50,P75,P100]				
Swollen Joints (66), n, Mean (SD), [P0,P25,P50,P75,P100]				
Enthesitis, n/N (%)				
SPARCC Enthesitis Count, n, Mean (SD), [P0,P25,P50,P75,P100]				
LEI Count, n, Mean (SD), [P0,P25,P50,P75,P100]				
Dactylitis, n/N (%)				
Dactylitis Count, n, Mean (SD), [P0,P25,P50,P75,P100]				
CDAI, n, Mean (SD), [P0,P25,P50,P75,P100]				
CDAI Category, n/N (%)				
Remission (CDAI $\leq$ 2.8)				
Low (2.8 < CDAI $\leq$ 10)				
Moderate (10 < CDAI $\leq$ 22)				
High (22 < CDAI)				
Minimal Disease Activity, n/N (%)				
DAPSA, n, Mean (SD), [P0,P25,P50,P75,P100]				
DAPSA Category, n/N (%)				
DAPSA $\leq$ 4				
4 < DAPSA $\leq$ 14				
14 < DAPSA $\leq$ 28				
28 < DAPSA				
cDAPSA, n, Mean (SD), [P0,P25,P50,P75,P100]				
cDAPSA Category, n/N (%)				
cDAPSA $\leq$ 3				
3 < cDAPSA $\leq$ 13				
13 < cDAPSA $\leq$ 27				
27 < cDAPSA				
PASDAS, n, Mean (SD), [P0,P25,P50,P75,P100]				
Nail VAS, n, Mean (SD), [P0,P25,P50,P75,P100]				
Body Surface Area (%), n, Mean (SD), [P0,P25,P50,P75,P100]				
BSA Category (%), n/N (%)				
0				
> 0 to < 3				
3 to < 10				
$\geq$ 10				

	Overall	Mono	Combo	p-value
CRP (mg/L), n, Mean (SD), [P0,P25,P50,P75,P100]				
ESR (mm/hr), n, Mean (SD), [P0,P25,P50,P75,P100]				
Patient Pain (0-100 VAS), n, Mean (SD), [P0,P25,P50,P75,P100]				
Patient Fatigue (0-100 VAS), n, Mean (SD), [P0,P25,P50,P75,P100]				
Patient Global Skin Assessment (0-100 VAS), n, Mean (SD), [P0,P25,P50,P75,P100]				
Clinical Global Assessment of PsO  , n, Mean (SD), [P0,P25,P50,P75,P100]				
Clinical Global Assessment of PsO  Category, n/N (%)				
Clear/Almost Clear				
Mild				
Moderate				
Severe				
HAQ-DI, n, Mean (SD), [P0,P25,P50,P75,P100]				
HAQ-S, n, Mean (SD), [P0,P25,P50,P75,P100]				
EQ-5D, n, Mean (SD), [P0,P25,P50,P75,P100]				
WPAI Domains (%), n, Mean (SD), [P0,P25,P50,P75,P100]				
Work Time Missed				
Impairment While Working				
Overall Work Impairment				
Activity Impairment				
Spinal Mobility Measures (cm), n, Mean (SD), [P0,P25,P50,P75,P100]				
Occiput to Wall Distance				
Modified Schober				

SD = standard deviation, P0 = minimum, P25 = 25th percentile, P50 = median, P75 = 75th percentile, P100 = maximum

a p-values from chi-square or Fisher exact tests for categorical variables and from Wilcoxon rank-sum tests for continuous variables, included for descriptive purposes only

b History of cardiovascular disease includes history of: hypertension, hyperlipidemia, cardiac revascularization procedure (CABG, stent, angioplasty), ventricular arrhythmia, cardiac arrest, myocardial infarction, acute coronary syndrome, unstable angina, CHF (with and without hospitalization), stroke, transient ischemic attack, other CV, deep vein thrombosis, peripheral arterial disease, peripheral arterial thrombosis, urgent peripheral revascularization, peripheral ischemia/gangrene, pulmonary embolism, carotid artery disease, and hemorrhage.

c Malignancy includes breast cancer, lung cancer, lymphoma, skin cancer (squamous cell), and other cancers.

d Serious infections include the following: joint/bursa infection, cellulitis, sinusitis, diverticulitis, sepsis, pneumonia, bronchitis, gastroenteritis, meningitis, urinary tract infection, upper respiratory infection, tuberculosis, and other infections.

e Biologics: Humira, Enbrel, Cimzia, Simponi, Remicade, Orencia, Taltz, Cosentyx, Stelara

f TNFs: Humira, Enbrel, Cimzia, Simponi, Remicade

g non-TNFs: Orencia, Taltz, Cosentyx, Stelara

h cDMARDs: MTX, Arava, Azulfidine, Otezla

 Clinical Global Assessment of PsO is scored on a five-point scale from 0-4, with corresponding interpretations of Clear, Almost Clear, Mild, Moderate, and Severe, respectively.

